## 5.2 Pre-Treatment Criteria

A new cycle of treatment may begin on the scheduled Day 1 of a new cycle if the following criteria are met within 24 hours of Day 1:

- ANC  $\geq 1,000/\text{mm}^3$  (growth factor support is permitted during cycles with the exception of Cycle 1 Day 1 (C1D1); it is allowed on the same day as treatment administration).
- Platelet count  $\geq 50,000/\text{mm}^3$  (platelet support is permitted during cycles of treatment; it is allowed on the same day as treatment administration, including C1D1).
- Any lenalidomide-related allergic reaction/hypersensitivity or sinus bradycardia/other cardiac arrhythmia AE that may have occurred has resolved to < Grade 1.
- Any other lenalidomide, carfilzomib, or isatuximab-related adverse event that may have occurred has resolved to <Grade 2.
- Herpes zoster lesions, if present, are dry.

If these conditions are not met on Day 1 of a new cycle, the subject will be evaluated weekly and a new cycle of therapy will not be initiated until the toxicity has resolved as described above. The maximum amount of time that treatment may be held for these toxicities to resolve is 3 weeks. If drug is held for more than 3 weeks due to toxicity, the patient is to discontinue all study treatment and enter the survival follow-up phase of the study.

For intra-cycle dosing on days where laboratory studies are scheduled, the following criteria must be met:

- Platelet count  $\geq 30,000$  (platelet transfusion support is permitted to meet criteria)
- Absolute neutrophil  $\geq 500/\text{mm}^3$  (growth factor support is permitted during cycles with the exception of Cycle 1 Day 1 (C1D1); it is allowed on the same day as treatment administration).

Intra-cycle dose modifications for all drugs will be allowed based on toxicity and according to dose modifications outline in Section 6.1, Table 9.

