Grade 2 – 3	Hold lenalidomide dose. Follow at least weekly. If the toxicity resolves to $\leq$ Grade 1 prior to Day 21, restart at 1 dose decrement and continue the cycle until Day 21.	Hold until $\leq$ Grade 1, reinstitute at current dose.
Grade 4	Discontinue	Discontinue

Toxicity	Recommended Action	
	Lenalidomide	Carfilzomib
Tumor lysis syndrome (≥ 3 of the following: ≥ 50% increase in creatinine, uric acid, or phosphate; ≥ 30% increase in potassium; ≥ 20% decrease in calcium; or ≥ 2-fold increase in LDH)	Hold lenalidomide until all abnormalities in serum chemistries have resolved. Reinstitute at full doses.	Hold carfilzomib until all abnormalities in serum chemistries have resolved. Reinstitute at full doses.
Infection Grade 3 or 4	Hold lenalidomide until systemic treatment for infection is completed. If no neutropenia, restart both drugs at full dose. If neutropenic, follow neutropenic instructions.	Hold carfilzomib until systemic treatment for infection is completed. If no neutropenia, restart both drugs at full dose. If neutropenic, follow neutropenic instructions.
Herpes zoster or simplex of any grade	Hold lenalidomide until lesions are dry. Reinstitute at full doses.	Hold carfilzomib until lesions are dry. Reinstitute at full doses.
Grade 2 neuropathy with pain or any Grade 3 neuropathy	Hold until ≤ Grade 2. Then restart lenalidomide at 1 dose decrement	Hold until resolved to ≤ Grade 2. Then restart carfilzomib at 1 dose decrement
Grade 4 neuropathy	Discontinue	Discontinue
Toxicity	Recommended Action	
	Lenalidomide	Carfilzomib
Renal dysfunction		
Serum creatinine > 2 mg/dL	Base dose reduction on calculated GFR (below)	Base dose reduction on calculated GFR (below)
CrCl > 50 mL/min	Full dose	Full dose
CrCl < 50 mL/min > 30 mL/min	Reduce lenalidomide to 10 mg every 24 h; may reinstate prior dose if, after 2 cycles, CrCl normalizes	Full dose

CrCl < 30 mL/min	Reduce lenalidomide to 15 mg every 48 h	Hold carfilzomib until CrCl > 30 mL/min; restart at 1 dose decrement
CrCl < 30 mL/min requiring dialysis	5 mg. Once daily. On dialysis days the dose should be administered following dialysis.	Hold until resolved to ≤ Grade 2. Then restart carfilzomib at 1 dose decrement
Venous thrombosis/embolism ≥ Grade 3	Hold lenalidomide dose and adjust anticoagulation regimen; re-start at Treating Investigator's discretion at full dose	No adjustment required

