
Pulmonary Toxicities: Interstitial Lung Disease (inc. pneumonitis), Acute Respiratory Failure, and Adult Respiratory Distress Syndrome (ARDS), cough and cough with phlegm
	
NA
	
≥ Grade 2 for Pneumonitis ≥ Grade 3 for ARDS ≥ Grade 4 for Respiratory Failure
 
Carfilzomib attribution, hold drug until resolved to ≤Grade 1. Resume at one level dose reduction

Blood clot in the lungs, fluid in the lungs, bleeding in the lungs
	
NA
	
≥ Grade 3: Carfilzomib attribution, hold drug until resolved to ≤ Grade 1. Resume at one level dose reduction

Gastrointestinal Perforation
	
NA
	
≥ Grade 3: Carfilzomib attribution, hold drug until resolved to Grade 1. Resume at one level dose reduction

Hepatic Toxicities (<math>\geq</math> Grade 3 elevation of AST or ALT, Bilirubin, or other <math>\geq</math> Grade 3 liver abnormalities)	Hold drug until resolved to $\leq$ Grade 1 or baseline. Resume at the same dose or reduced dose as appropriate. If tolerated, the reduced dose may be escalated to the previous dose at the discretion of the physician. Frequent monitoring of liver function should then be implemented.	Hold drug until resolved to $\leq$ Grade 1 or baseline. Resume at the same dose or reduced dose as appropriate. If tolerated, the reduced dose may be escalated to the previous dose at the discretion of the physician. Frequent monitoring of liver function should then be implemented. Please see additional information on hepatic impairment in Table 9
Other non-hematologic toxicity assessed as lenalidomide-related <math>\geq</math> Grade 3	Hold lenalidomide dose. Follow at least weekly. If the toxicity $\leq$ Grade 1 before Day 21 of the current cycle, restart at 1 dose decrement and continue until Day 21 of the current cycle	Full dose
Other non-hematologic toxicity assessed as carfilzomib-related	Full dose	Hold carfilzomib dose until toxicity resolves to $\leq$ Grade 1 or baseline. Restart at 1 dose decrement
Other non-hematologic toxicity assessed as drug-related <math>\geq</math> Grade 3	Hold treatment and restart at 1 dose decrement when toxicity has resolved to $\leq$ Grade 1 or baseline	Hold treatment and restart at 1 dose decrement when toxicity has resolved to $\leq$ Grade 1 or baseline

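### For Grade ≥3 liver toxicity attributable to carfilzomib, Table 9 allows the drug to resume where Table 10 stops it; two other overlaps in Table 9 need a pointer

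*Combined protocol and SAP*

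**What the plan says.** Section 6 says that dose changes will follow its tables. Three places in Section 6.1 matter here, all for carfilzomib.

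- **Liver.** The Table 9 hepatic row covers Grade ≥3 AST, ALT, bilirubin or other liver abnormalities. Carfilzomib is held until Grade 1 or baseline. Then: "Resume at the same dose or reduced dose as appropriate". A reduced dose that is tolerated may go back up at the physician's discretion. The row sets no condition on cause and ends "Please see additional information on hepatic impairment in Table 9". Table 10, in its hepatic impairment entry, stops carfilzomib when the hepatotoxicity is attributable to it, with no grade stated.
- **Pulmonary embolism.** The Table 9 row "Venous thrombosis/embolism", at Grade ≥3, says "No adjustment required" for carfilzomib, again with no condition on cause. A later row, "Blood clot in the lungs, fluid in the lungs, bleeding in the lungs", applies at Grade ≥3 with carfilzomib attribution: hold to Grade 1 or lower, then resume one dose level lower.
- **Arrhythmia.** One Table 9 row (sinus bradycardia and other arrhythmias) holds carfilzomib at Grade ≥3 and restarts it at the current dose, without asking about cause. Another (heart problems, including irregular heartbeat) restarts it one level lower if the event is attributed to carfilzomib.

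Section 5.1 sends carfilzomib dosing in hepatic impairment to Table 10. Section 5.2 sends intra-cycle modifications of all drugs to Table 9.

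**The concern.** The liver instructions differ in kind: one permits rechallenge and the other stops the drug. A site that follows the Table 9 row as printed can give carfilzomib again to a participant whose liver injury it has already attributed to carfilzomib. The cross-reference that should lead the reader to the stopping rule leads back to the same table.

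The choice has a further consequence. Under Treatment Discontinuation in Section 6.1, permanent discontinuation of carfilzomib before Cycle 4 ends the participant's treatment after Cycle 4. The table a site opens can therefore decide whether that participant continues on protocol therapy.

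The embolism and arrhythmia overlaps matter less, but they leave the restart dose to whichever row is read first. Safety and tolerability is a secondary objective, and Section 12.1 will summarise dose reductions and adverse events leading to reduction, interruption or discontinuation. Inconsistent row choice would carry into those summaries.

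**Working it through.** The check is mainly a comparison of text. The arithmetic only sizes the gaps.

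**Inputs.** Carfilzomib levels are 56 mg/m² (starting) and 45 mg/m² (one level down), from Section 6.1. Dosing days are 1, 8 and 15 in induction and 1 and 15 in high-risk maintenance, with no carfilzomib in standard-risk maintenance (Section 5.3.2.6 and Table 13). All figures assume that the participant is at 56 mg/m² when the event occurs.

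**Step 1: does one event meet both rules?**

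| Event, Grade ≥3, attributed to carfilzomib | Rule A | Rule B | Can one action satisfy both? |
|---|---|---|---|
| Hepatotoxicity | Table 9: hold, then resume at same or lower dose | Table 10: stop | No |
| Pulmonary embolism | Thrombosis row: no change | Lung-clot row: hold, then one level lower | Only if no change required is read as permitting a hold and reduction |
| Arrhythmia | Arrhythmia row: hold, restart at current dose | Irregular heartbeat row: hold, restart one level lower | On the hold, yes; on the restart dose, no |

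A page split breaks the layout of Table 10, but its last trigger (attributable hepatotoxicity) still pairs with its last action (stop). Its other hepatic actions make resumption or re-escalation depend on drug-induced injury having been ruled out, which supports that pairing.

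**Step 2: does any text rank the rules?** Section 6 refers to the tables without ranking them. Section 5.1 favours Table 10 for hepatic impairment, Section 5.2 favours Table 9 for changes within a cycle, and the hepatic row cites itself. Treatment Discontinuation lets the treating investigator stop a drug for treatment-related toxicity but does not reconcile the tables. Nothing mentions the paired embolism or arrhythmia rows.

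**Step 3: do the cycle-start criteria settle the liver case?** Section 5.2 requires, before a new cycle: "Any other lenalidomide, carfilzomib, or isatuximab-related adverse event that may have occurred has resolved to <Grade 2". Liver values back at Grade 1 or lower meet that condition, so it delays rechallenge but does not prevent it. The three-week limit on toxicity holds narrows the conflict mainly to participants who recover within three weeks, although Section 6.1 leaves longer delays and re-treatment to the Principal Investigator.

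**Step 4: size.**

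- Attributable hepatotoxicity, after recovery: up to 56 mg/m² per dose (Table 9) or 0 (Table 10). Over a three-dose cycle, up to 3 × 56 = 168 or 0. Over a high-risk maintenance cycle, up to 2 × 56 = 112 or 0.
- Embolism and arrhythmia, restart level: 56 − 45 = 11 mg/m² per dose, and 11/56 = 19.6%. Over a three-dose cycle, 168 − (3 × 45 = 135) = 33 mg/m². Over a high-risk maintenance cycle, 112 − (2 × 45 = 90) = 22 mg/m². In standard-risk maintenance, 0.

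**Step 5: which other liver events does Table 10 list?** It lists Grade 3 bilirubin, and it lists raised AST or ALT with normal bilirubin on two consecutive readings 28 days or more apart. The second entry sits under a mild-to-moderate label, but its definition has no upper grade limit. A 25% reduction gives 0.75 × 56 = 42 mg/m², which Table 9 also permits. These entries do not contradict Table 9, but any rule of precedence has to cover them.

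**The case against.** The strongest reply is that a careful reader can reconcile most of this.

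On the liver, Section 5.1 names Table 10, that table presents itself as additional carfilzomib modifications, and the self-reference in Table 9 is evidently a wrong number. That stands as an account of what was probably intended. It does not remove the Table 9 permission to resume whatever the cause, and Section 5.2 points to Table 9.

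On embolism and arrhythmia, the Table 9 rows from hypertension to gastrointestinal perforation form a carfilzomib block: the lenalidomide cell is not applicable and the carfilzomib action depends on attribution. The lung-clot and irregular-heartbeat rows belong to it and read naturally as the specific exceptions. Section 5.2 also treats arrhythmia as a lenalidomide category: "Any lenalidomide-related allergic reaction/hypersensitivity or sinus bradycardia/other cardiac arrhythmia AE". This largely stands. What is missing is a sentence saying so.

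The columns are also headed as recommendations, and investigators may stop a drug at their discretion. Both points lower the risk without resolving the liver conflict.

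Two stronger readings are tempting. From "For intra-cycle dosing on days where laboratory studies are scheduled, the following criteria must be met", followed only by platelet and neutrophil limits, a reader might infer that nothing stops the doses still due in a cycle after an embolism attributed to carfilzomib. The documents do not support that: the next sentence of Section 5.2 refers intra-cycle changes to Table 9, which contains the lung-clot hold. A reader might also count Grade 3 bilirubin, with drug-induced injury excluded, as a further contradiction. It is not one, because a 25% reduction complies with both tables.

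**Conclusion.** The liver conflict holds and is wrong as written. For Grade ≥3 hepatotoxicity attributable to carfilzomib, one table permits up to 56 mg/m² per dose after recovery and the other permits none, and no text settles which applies. The embolism and arrhythmia overlaps are real but secondary: they are clarifications worth 11 mg/m² (19.6%) per dose at restart, and the sensible reading is already available.

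This rests on a starting level of 56 mg/m², on the site attributing the event to carfilzomib, and on the pairing of trigger and action in Table 10 described above. The documents give no incidence for these events under this regimen, so the number of participants affected cannot be estimated.

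A reader might infer that the primary complete-response result is in doubt. Nothing here supports that: the sample size, power and decision rule do not depend on these rows.

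**What to change.** Amend the carfilzomib column of three Table 9 rows.

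1. **Hepatic row.** Change the cross-reference to Table 10. Add that carfilzomib is discontinued if the hepatotoxicity is attributable to it. State that Table 10 governs every hepatic event it lists, including Grade 3 bilirubin and raised AST or ALT with normal bilirubin on two readings at least 28 days apart, and that the Table 9 row applies only to events meeting no Table 10 entry.
2. **Venous thrombosis/embolism row.** Add that a Grade ≥3 pulmonary embolism attributed to carfilzomib follows the lung-clot row. Other venous thrombosis keeps the present instruction.
3. **Arrhythmia row.** Add that a Grade ≥3 event attributed to carfilzomib follows the irregular-heartbeat row.

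The cost is a text change in the next amendment, with no added procedures or participants.

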**Table 10. Additional Carfilzomib Dose modifications and Safety Measures:**

Hepatic Impairment
 
Mild to moderate liver dysfunction defined as 2 consecutive values at least 28 days apart, of:
 
-Total bilirubin (>33%) > 1x ULN or <3x ULN OR
 
-An elevation of AST and/or ALT with normal bilirubin
	
-25% dose reduction. Dose may be re-escalated if liver function tests return to normal and drug-induced hepatotoxicity is excluded.
 
-Hold carfilzomib until resolution to baseline. Resume with a 25% dose reduction if drug-induced hepatotoxicity is excluded. Monitor bilirubin and direct

---	---

-Grade 3 elevation in total bilirubin
 
-Drug-induced hepatotoxicity (attributable to carfilzomib)
	
bilirubin weekly.
 
-Upon resolution of total bilirubin to normal, resume carfilzomib doing with 25% dose reduction if drug-induced hepatotoxicity is excluded.
 
-Discontinue carfilzomib

Posterior Reversible Encephalopathy Syndrome (PRES)
	
If PRES is suspected, hold carfilzomib, Consider MRI for onset of visual or neurological symptoms suggestive of PRES. If PRES confirmed, permanently discontinue carfilzomib. If PRES excluded, carfilzomib administration may resume at same dose if clinically appropriate.

Thrombotic Microangiopathy (TMA)
	
If the diagnosis is suspected, hold carfilzomib and manage per standard of care including plasma exchange as clinically appropriate. If TMA confirmed, permanently discontinue carfilzomib. If TMS excluded, carfilzomib can be restarted.

Contraception/Female
	
Females of child-bearing potential and/or their male partners should use effective contraception methods or abstain from sexual activity during and for 30 days after treatment with carfilzomib.

Contraception/Male
	
Males and/or their female partners should use effective contraceptive methods or abstain from sexual activity while treated with carfilzomib and for 90 days after treatment.

Breastfeeding/Lactation
	
Breastfeeding women and women planning on breastfeeding may not participate in the clinical trial


Hepatitis B reactivation
	
Carriers of HBV who require treatment with Kyprolis should be closely monitored for signs and symptoms of active HBV infection throughout treatment. Any subject who becomes HBV DNA positive or develops reactivation of HBV should have carfilzomib treatment interrupted and receive appropriate anti-viral treatment as per a specialist in Hepatitis B.

Progressive Multifocal Leukoencephalopathy
	
Patients should be monitored for any new or worsening neurologic, cognitive or behavioral signs or symptoms that may be suggestive of PML as part of the differential diagnosis of CNS disorders. If PML is suspected, patients should be promptly referred to a specialist and appropriate diagnostic testing should be initiated. Discontinue Kyprolis if PML diagnosis is confirmed.

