  - f) total bilirubin  $\leq 2.0 \times$  ULN, except in subjects with congenital bilirubinemia, such as Gilbert syndrome (direct bilirubin  $\leq 2.0 \times$  ULN)
  - g) creatinine clearance  $\geq 30$  mL/min
  - h) corrected serum calcium  $\leq 14$  mg/dL ( $\leq 3.5$  mmol/L); or free ionized calcium  $< 6.5$  mg/dL ( $< 1.6$  mmol/L).
6. Women of childbearing potential must commit to either abstain continuously from heterosexual sexual intercourse or to use 2 methods of reliable birth control simultaneously. This includes one highly effective form of contraception (tubal ligation, intrauterine device [IUD], hormonal [birth control pills, injections, hormonal patches, vaginal rings or implants] or partner's vasectomy) and one additional effective contraceptive method (male latex or synthetic condom, diaphragm, or cervical cap). Contraception must begin 4 weeks prior to dosing. Reliable contraception is indicated even where there has been a history of infertility, unless due to hysterectomy or bilateral oophorectomy.
7. A man who is sexually active with a woman of childbearing potential must agree to use a latex or synthetic condom, even if they had a successful vasectomy. All men must also not donate sperm during the study, for 4 weeks after the last dose of lenalidomide, for 90 days after the last dose of carfilzomib, and for 4 months after the last dose of isatuximab.
8. A woman of childbearing potential must have 2 negative serum or urine pregnancy tests at Screening, first within 10 to 14 days prior to dosing and the second within 24 hours prior to dosing.
9. Each subject (or their legally acceptable representative) must sign an informed consent form (ICF) indicating that he or she understands the purpose of and procedures required for the study and are willing to participate in the study. Subject must be willing and able to adhere to the prohibitions and restrictions specified in this protocol, as referenced in the ICF.

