### **5. TREATMENT PLAN**

#### **5.1 Treatment Regimen**

Carfilzomib, lenalidomide, dexamethasone, and isatuximab will be administered on a 28-day treatment cycle. All subjects will perform stem cell collection after 4 cycles of therapy.

For patient undergoing upfront stem cell transplant (SCT):

4 cycles of therapy followed by stem cell collection, high-dose chemotherapy, and autologous SCT followed by 2 additional cycles of therapy then maintenance.

For patients deferring SCT following collection:

4 cycles of therapy followed by stem cell collection followed by 4 additional cycles of therapy then maintenance.

Carfilzomib 56 mg/m^2 IV on Days 1, 8, 15

Lenalidomide 25 mg orally (po) on Days 1-21

Isatuximab 10 mg/kg IV Q1 week for 8 weeks, then Q2 weeks for 16 weeks, thereafter Q4 weeks

Dexamethasone 20 mg po will be administered day of and day after all doses of carfilzomib (Days 1, 2, 8, 9, 15, and 16) and isatuximab (Cycles 1 and 2 Days 22 and 23). The dexamethasone 20 mg oral or IV dose administered as a preinfusion medication on isatuximab infusion days (Days 1, 8, 15, 22) replaces the oral dexamethasone dose for that day.

\*All subjects with receive carfilzomib 20 mg/m^2 on Day 1 Cycle 1

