**Maintenance:**

Patients must achieve a PR or better to continue onto maintenance therapy on the study.

28-day Maintenance Cycle until progressive disease (PD) or unacceptable toxicity. Subjects will be stratified based on cytogenetics (deletion (del) 17, translocation (t)(4:14), t(14;16), t(14;20), 1q duplication).

Standard-risk:

Lenalidomide 10 mg po Days 1-21

High-risk:

Carfilzomib 56 mg/m^2 (or last tolerated dose) IV Days 1, 15

Lenalidomide 10 mg po Days 1-21

Isatuximab 10 mg/kg IV Day 1 for up to 24 cycles of maintenance (two years), then discontinue

In the maintenance phase, dexamethasone, 20 mg orally or IV will be administered to subjects as a preinfusion medication prior to isatuximab dosing. When dexamethasone is reduced to 20 mg/week and is given as preinfusion medication, subjects may receive low-dose methylprednisolone ( $\leq 20$  mg) orally (or equivalent in accordance with local standards) for the prevention of delayed infusion-associated reactions (IARs), as clinically indicated.

Because lenalidomide is primarily excreted unchanged by the kidney, adjustments to the starting dose of lenalidomide are recommended to provide appropriate drug exposure in patients with renal impairment. Lenalidomide dose adjustment should be instituted for patients with a CrCl  $\leq 50$  mL/min. The recommended doses for patients with multiple myeloma and renal impairment are shown below in Table 9. If during treatment a patient's renal status changes, the dose should be adjusted as shown in Table 9. Similarly, adjustments to the starting and ongoing dosing of carfilzomib are recommended in the setting of hepatic impairment. The doses should be adjusted as shown in Table 10.

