### 8. STUDY CALENDAR

Baseline evaluations are to be conducted within 28 days prior to start of protocol therapy. Scans and x-rays must be done  $\leq 4$  weeks prior to the start of therapy. In the event that the participant's condition is deteriorating, laboratory evaluations should be repeated within 48 hours prior to initiation of the next cycle of therapy.

Assessments must be performed prior to administration of any study agent. Study assessments and agents should be administered within  $\pm 8$  days of the protocol-specified date, unless otherwise noted.

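### Table 10's mild-to-moderate hepatic rule for carfilzomib has a bilirubin range that excludes no value, and its 28-day persistence test is too slow to set the starting dose for most screening dates

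*Combined protocol and SAP*

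**What the plan says.** Table 10 (Section 6.1) gives the rule as "Mild to moderate liver dysfunction defined as 2 consecutive values at least 28 days apart, of" one of two limbs. The first is total bilirubin, with an unexplained (>33%), above 1x ULN *or* below 3x ULN. The second is "An elevation of AST and/or ALT with normal bilirubin". Grade 3 bilirubin and hepatotoxicity attributable to carfilzomib are listed separately. Read in order, the first action is a 25% dose reduction, with re-escalation allowed.

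Section 5.1, in the text under Maintenance, states: "Similarly, adjustments to the starting and ongoing dosing of carfilzomib are recommended in the setting of hepatic impairment". It continues: "The doses should be adjusted as shown in Table 10".

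On timing, Section 8 states: "Baseline evaluations are to be conducted within 28 days prior to start of protocol therapy". Section 5.1 says the regimen "will be administered on a 28-day treatment cycle". Table 14 schedules chemistries on Days 1, 8, 15 and 22 of Cycles 1-2 and on Days 1 and 15 of the later induction and consolidation cycles. The dose list in Section 6.1 gives the carfilzomib starting dose as 56 mg/m2, with 20 mg/m2 on Cycle 1 Day 1.

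On entry, Section 3.1 admits AST and ALT up to 2.5x ULN and total bilirubin up to 2.0x ULN, "except in subjects with congenital bilirubinemia, such as Gilbert syndrome", for whom the limit applies to direct bilirubin.

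**The concern.** This is an operative dosing rule, and two parts of it do not do what the protocol evidently intends.

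First, a threshold that every value meets is not a threshold. Taken literally, the bilirubin limb takes in normal patients, makes the AST/ALT limb redundant and overlaps the separate Grade 3 entry.

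Second, Section 5.1 says the starting dose is to be adjusted for hepatic impairment, but the only rule it points to needs two results at least 28 days apart. Patients with mild elevation are eligible, so the rule has people to act on, and for most of them the evidence it needs arrives after dosing has begun. Sites are then left to choose between the intent in Section 5.1 and the wording of Table 10, and can dose similar patients differently while each follows the protocol.

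**Working it through.** The plan states no figure on this point, so there is none to reproduce. The check is one of logic and dates.

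**Bilirubin limb.** To fail (above 1) *or* (below 3), a value would have to be at most 1 and at least 3, which is impossible. At 0.5, 1, 1.5, 2, 3 and 5x ULN, *or* is met by 6 of 6 and *and* by 2 of 6 (1.5 and 2). On a grid of 2001 values from 0 to 20x ULN, *or* excludes none, while *and* keeps only 1.01 to 2.99. The (>33%) might refer to a bilirubin fraction, but the text does not say of what, and it sets no limit on total bilirubin.

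**Starting dose.** Inputs: the 28-day gap (Table 10), the baseline window of Day -28 to Day -1 (Section 8), the nominal chemistry days (Table 14) and carfilzomib on Days 1, 8 and 15 (Section 5.1). Count Cycle 1 Day 1 as day 0, so that screening on Day -s and a draw on day t are s + t days apart.

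- Before Cycle 1 Day 1 (t = 0): s >= 28, so Day -28 only, 1 of 28 dates.
- Before the first 56 mg/m2 dose (Cycle 1 Day 8, t = 7): s >= 21, so Days -28 to -21, 8 of 28 dates. For Days -27 to -21 the screening value must be compared with Day 8 across the Cycle 1 Day 1 draw, which means that *consecutive* cannot mean adjacent.

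The table allows non-adjacent comparison. It assumes a persistent elevation, draws taken before dosing, and that the 25% cut is the action for this row (20 becomes 15, 56 becomes 42).

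| Screening day | Dates | First qualifying draw | Given unadjusted (mg/m2) | Excess over a 25% cut |
|---|---|---|---|---|
| -28 | 1 | C1D1 | 0 | 0 |
| -27 to -21 | 7 | C1D8 | 20 | 20 - 15 = 5 |
| -20 to -14 | 7 | C1D15 | 20 + 56 = 76 | 76 - 57 = 19 |
| -13 to -7 | 7 | C1D22 | 20 + 56 + 56 = 132 | 132 - 99 = 33 |
| -6 to -1 | 6 | C2D1 | 132 | 33 |

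On 20 of 28 dates at least one 56 mg/m2 dose is given before the rule can apply.

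**Ongoing dose.** Chemistry days in Cycles 1-4 are 0, 7, 14, 21, 28, 35, 42, 49, 56, 70, 84 and 98. The 11 adjacent gaps are 7 days (eight times) or 14 days (three times), and none reaches 28. Day 1 of Cycle 1 and Day 1 of Cycle 2 are exactly 28 days apart. The rule therefore works during induction if Day 1 values of successive cycles are compared, and nominally does not fire in Cycles 1-4 if *consecutive* means adjacent. The text does not say which.

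**The case against.** The strongest reply is that these are drafting slips with little clinical reach. The row is headed mild to moderate, the second limb deals with normal bilirubin separately, and Grade 3 has its own entry, so a clinician would read *and*. That is fair. A reader might infer that sites would cut carfilzomib in patients with normal bilirubin; the table's own structure argues against it. The written threshold is still wrong.

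On the starting dose, a reader might infer that only Day -28 can ever work. That is too strong. The starting dose is defined as 56 mg/m2, first given on Cycle 1 Day 8, which brings in Days -27 to -21. Table 10 does not forbid pre-study values, and Section 5.1 only recommends adjustment. Section 3 and Table 14 also count screening from enrollment or registration, though Section 8 caps baseline at 28 days before therapy. These routes narrow the gap but do not close it, because no passage requires or mentions pre-study liver values.

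A reader might also infer that the rule is void for ongoing dosing. It is not. Day 1 values of successive cycles satisfy it, and in maintenance, if the single chemistry mark per cycle means one draw, even adjacent values are 28 days apart. This part is a clarification.

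Finally, a reader might see Tables 9 and 10 as prescribing different doses after Grade 3 bilirubin. The row alignment of Table 10 cannot be read from the available text, so no such conflict is claimed.

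**Conclusion.** The point holds as a wording defect in a dosing rule that should be corrected. The bilirubin limb excludes no value of total bilirubin. The persistence test can inform the dose before Cycle 1 Day 1 on 1 of 28 screening dates, and before the first 56 mg/m2 dose on 8 of 28 at most, unless pre-study values are used.

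The reach is limited to mild elevation not attributed to carfilzomib. Before a new cycle, Section 5.2 requires: "Any other lenalidomide, carfilzomib, or isatuximab-related adverse event that may have occurred has resolved to" below Grade 2. Table 9 holds carfilzomib and lowers it one level for related non-hematologic toxicity, and holds it for hepatic events of Grade 3 or higher. Table 10 lists discontinuation for hepatotoxicity attributable to carfilzomib. With non-adjacent values compared, the illustrated excess is 0 to 33 mg/m2, all within Cycle 1.

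These figures assume nominal visit days (Section 8 allows 8 days either side), no holds, and the 25% cut as the action for this row. The number of affected patients is not given. The sample size and primary test in Section 12.1 do not depend on this rule, and the documents do not support inferring an effect on the CR rate.

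**What to change.** 1. In Table 10, write the bilirubin limb as above 1x ULN *and* below 3x ULN, and explain or remove (>33%).
2. In Section 5.1, either delete *starting*, or have the clinical team set a trigger based on the screening value.
3. Keep the persistence requirement for ongoing dosing, but word it as abnormal on two occasions at least 28 days apart, for example Day 1 of successive cycles. Since that interval is exactly 28 days, say that a Day 1 sample drawn the day before still counts, and whether intervening results must also be abnormal.
4. As a clerical tidy-up, point Table 9's hepatic row to Table 10; it now refers to Table 9.

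The cost is amendment wording. A screening-value trigger would be a clinical dosing decision. No new tests, visits or patients are needed.
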